8.3 Methods for Handling Missing Data

If AK lesion counts are missing at post-baseline visits, depending on the reason for the early discontinuation, the following rules will be applied:

- For subjects who are discontinued prematurely due to worsening condition that requires alternate or supplemental therapy for the treatment of AK, or who are discontinued prematurely after completing at least four weeks of treatment due to lack of treatment effect, they will be included in the mITT and PP populations and considered as treatment failures.
- For subjects who are discontinued prematurely for any other reasons, Last Observation Carried Forward (LOCF) imputation will be used to impute the missing data. They will be included in the mITT population, but excluded from the PP population.

8.4 Subject Disposition

Subjects who complete the 60 days of treatment and all of the EOS visit evaluations at Day 90 will be considered to have completed the study.

The number and percent of subjects who were enrolled in the study, who completed the study, and who withdrew from the study will be tabulated by treatment group for the Safety, mITT and PP populations along with their reasons for discontinuation.

Subjects who are excluded from the mITT or the PP population with their reasons for exclusion will be listed.

Subjects who were screen failures with their reason for screen failure will be listed.

8.5 Screening and Baseline Assessments

8.5.1 *Demographic and Baseline Characteristics*

Gender, age, race and ethnicity will be summarized by treatment group for the Safety, mITT and PP populations.

Characteristics of the AK lesions in the Treatment Area at Baseline will be summarized including the location, total number of AK lesions and the number of AK lesions at least 4 mm in diameter.

Informed consent information and subject eligibility status will be provided in a listing.

8.5.2 *Medical History*

Medical history at Screening/Baseline will be presented in a subject data listing for the Safety population.

8.5.3 *Prior Medications*

Listings will be provided for the prior medications that were taken and stopped prior to the randomization date.

8.6 Efficacy Analyses

8.6.1 *Primary Efficacy Analyses*

The primary efficacy endpoint is the proportion of subjects in the PP population with treatment success (“Complete Clearance”) at Day 90 (30 days after completion of 60 days of treatment), where Complete Clearance is defined as 100% clearance of all AK lesions (having a count of zero AKs) in the 25 cm² treatment area (face or bald scalp) at the Day 90 visit.

Subjects who discontinued early from the study due to lack of treatment effect after completing at least four weeks of treatment or who worsen and require alternate or supplemental therapy will be included in the PP and the mITT populations as treatment failures (non-responders). For subjects who are discontinued prematurely for any other reasons, LOCF imputation will be used to impute missing data in the mITT population.

Test for bioequivalence of test and reference treatments

To establish bioequivalence for the proportion of subjects with treatment success, the following hypotheses will be tested in the PP population:

$$H_0: \pi_T - \pi_R < -0.2 \text{ or } \pi_T - \pi_R > 0.2$$

$$H_A: -0.2 \leq \pi_T - \pi_R \leq 0.2$$

, where π_T is the proportion of subjects with treatment success in test treatment group (GDC 695 (diclofenac sodium gel, 3%)) and π_R is the proportion of subjects with treatment success in reference treatment group (Diclofenac Sodium Gel, 3% (Fougera)).

The null hypothesis, H_0 , is rejected with a type I error (alpha) of 0.05 (two one-sided tests) if the estimated 90% Wald's confidence interval with Yate's continuity correction for the difference of the success rates between test and reference treatment groups ($\pi_T - \pi_R$) is contained within the interval $[-0.2, 0.2]$. Rejection of the null hypothesis supports the conclusion of equivalence of the test and reference treatments.

This analysis will be repeated for mITT population as a supportive analysis.

Test for superiority of each active treatment over vehicle treatment

To establish that the study is sufficiently sensitive to detect the difference between treatments, two-sided, continuity-corrected chi-square tests with an alpha of 0.05 will be used to test the superiority of each active treatment group's treatment success rate over that of the Vehicle treatment in the mITT population. If any cells have an expected frequency of less than 5, then Fisher's exact tests will be used instead.

This analysis will be repeated for PP population as a supportive analysis.

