NAMES AND ADDRESSES OF DEPARTMENTS AND/OR INSTITUTIONS INVOLVED IN THE STUDY

Test Article Labeling:

[REDACTED]

Institutional Review Board:

[REDACTED]

PROTOCOL SYNOPSIS

Title	A Multicenter, Randomized, Double-Blind, Placebo-Controlled, Parallel Group Comparison Study to Determine the Therapeutic Equivalence of GDC 695 and Diclofenac Sodium Gel, 3% in Subjects with Actinic Keratoses
Study Type	Bioequivalence with Clinical Endpoint
Test Articles	1. Test product: GDC 695 (Gage Development Company, LLC) 2. Reference Listed Drug (RLD): Diclofenac Sodium Gel, 3% (Fougera) 3. Placebo: vehicle gel (Gage Development Company, LLC)
Study Objective	To evaluate the safety and therapeutic equivalence of GDC 695 to Diclofenac Sodium Gel, 3% and to establish the superiority of the efficacy of these two products over the vehicle gel (i.e., placebo) in the treatment of actinic keratoses (AK).
Study Design	Multicenter, randomized, double-blind, placebo-controlled, parallel group comparison.
Treatment Groups	Eligible subjects will be randomized (1:1:1) to treatment with GDC 695, Diclofenac Sodium Gel, or placebo.
Duration of Treatment	Twice-daily application for 60 days.
Duration of Study	Approximately 90 days (not including a maximum 30-day screening period).
Study Population	Male and/or female subjects, ages 18 years and older with actinic keratoses on the face or bald scalp.
Total Number of Subjects	Approximately 600 subjects will be enrolled to obtain at least 558 modified intent-to-treat (mITT) and at least 417 per-protocol (PP) subjects in the study.
Number of Sites	Approximately 28 sites will participate in the study.
Inclusion Criteria	To enter the study, a subject must meet the following criteria: 1. Is an immunocompetent male and/or non-pregnant female, 18 years of age or older. 2. Has provided written informed consent including consent to photography of the treatment area at Visit 1. 3. Is willing and able to apply the test article(s) as directed, comply with study instructions, and commit to all follow-up visits for the duration of the study. 4. Has a clinical diagnosis of actinic keratoses with at least five (5) and no more than ten (10) clinically typical, visible, or palpable, discrete, nonhyperkeratotic, nonhypertrophic, AK lesions, each at least 4 mm in

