7. RANDOMIZATION ASSIGNMENT

Subjects who are eligible for enrollment into the study will be randomized by assigning the lowest subject kit number available at the site. Subjects will be randomized to one of three treatments on a 1:1:1 basis [GDC 695 (Gage), Diclofenac Sodium Gel, 3% (Fougera), or vehicle gel (Gage), respectively].

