17.3.1 Efficacy Analyses

The 90% Wald's confidence interval with Yate's continuity correction will be constructed on the difference between the proportions of subjects with AK lesion clearance in the Test and Reference treatments to evaluate the therapeutic comparability of the two active treatments. Evaluation in the PP population will be considered primary.

At Day 90 (30 days after completion of 60 days of treatment), if the 90% confidence interval on the difference between the Test and Reference lesion clearance proportions

are contained within the interval -0.20 to +0.20, then the Test and Reference products will be considered to be therapeutically equivalent.

Two-sided, continuity-corrected Chi-square tests will be used to evaluate the superiority of each active treatment's complete clearance proportion over that of the Vehicle treatment in the mITT population using LOCF.

The therapeutic comparability evaluations in the PP population will be considered primary, while those in the mITT population will be considered supportive. The superiority comparisons in the mITT population will be considered primary while those in the PP population will be considered supportive.

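### The superiority tests are valid but make no use of baseline AK count; stratifying on it is a small, nearly free improvement

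*SAP*

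**What the plan says.** Protocol section 17.3.1 (repeated in the synopsis) states: "Two-sided, continuity-corrected Chi-square tests will be used to evaluate the superiority of each active treatment's complete clearance proportion" over vehicle in mITT with LOCF. SAP section 8.6.1 repeats this ("two-sided, continuity-corrected chi-square tests with an alpha of 0.05 will be used to test the superiority of each active" group over vehicle) and adds a small-cell rule: "If any cells have an expected frequency of less than 5, then Fisher's exact tests will be used instead". It gives the purpose as "To establish that the study is sufficiently sensitive to detect the difference between treatments". Neither document adds a stratified, covariate-adjusted or sensitivity version, and SAP section 8.12 plans no subgroup analyses.

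Success is a count of zero AKs in the treatment area at Day 90, new lesions included (protocol 17.2.1). Eligible subjects have at least five lesions of 4 mm or more (protocol 5.1.1) and at most ten of any size (5.1.2). All lesions are counted at baseline (protocol 10.1, SAP 7.1.1). In the analysis this information is only described: SAP 8.5.1 summarises location, "total number of AK lesions and the number of AK lesions at least 4 mm in diameter", and Tables 14.1.4.1 to 14.1.4.3 present it by population.

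On allocation, protocol section 7 says "Subjects will be randomized to one of three treatments on a 1:1:1 basis", with subjects "randomized by assigning the lowest subject kit number available at the site". No stratification by count or location is stated.

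**The concern.** A subject who enters with ten lesions must clear all ten, and one who enters with five must clear five. For the same chance of clearance per lesion, the first task is harder. Entry count may therefore explain part of the variation in outcome, and neither the allocation nor the analysis takes account of it.

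Two things are at stake, both modest. The first is a little power in each superiority test. The sample-size text asks for equivalence and superiority of both actives together, so each test has to succeed. The second is chance imbalance in count. It matters more for the Test-Reference comparison in PP, because PP exclusions for compliance, visit window and violations occur after randomisation and can disturb balance. If imbalance appears and nothing was planned, any adjustment would have to be labelled unplanned under SAP section 2.

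**Working it through.** **Inputs from the documents.** The synopsis says: "Approximately 600 subjects will be enrolled to obtain at least 558 modified intent-to-treat (mITT) and at least 417 per-protocol (PP) subjects". With equal arms this is 558/3 = 186 per arm in mITT and 417/3 = 139 per arm in PP. PP keeps 417/600 = 69.5% of those enrolled. The planning rates and power are redacted, so the sample size cannot be reproduced. Everything below rests on assumed rates.

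**Step 1: how strongly could count matter?** Assume 30% overall success and counts uniform on 5-10. If lesions clear independently with probability q, then P(clear | n) = qⁿ. Setting the average over n = 5 to 10 to 0.30 gives q ≈ 0.847.

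- Independent lesions: P(clear) falls from 0.44 at five lesions to 0.19 at ten.
- Within-subject correlation 0.4 (beta-binomial): it falls from 0.36 to 0.26.
- Share of outcome variance explained, Var[P(clear | n)] / [0.30 × 0.70]: 3.4% at correlation 0 and 0.2% at correlation 0.6.

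This models baseline lesions only; new lesions are not modelled.

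**Step 2: the planned test.** Exact power of the continuity-corrected chi-square at 186 per arm is 88.2% (active 25%, vehicle 12%), 73.9% (30%, 18%) and 88.3% (35%, 20%).

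**Step 3: gain from stratifying.** Simulation, 4,000 trials per cell: continuity-corrected Mantel-Haenszel, strata of count (5-6, 7-8, 9-10) by location. Assumed: 30% scalp, location odds ratio 0.7, counts skewed toward five. Entries are power, unadjusted → stratified.

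| Active / vehicle | OR per extra lesion 1.00 | 0.85 | 0.75 | 0.65 |
|---|---|---|---|---|
| 25% / 12% | 88.7 → 88.6 | 88.1 → 87.9 | 87.8 → 88.2 | 88.0 → 88.9 |
| 30% / 18% | 72.5 → 72.4 | 73.7 → 73.6 | 73.7 → 74.9 | 73.4 → 75.5 |
| 35% / 20% | 89.2 → 88.8 | 88.0 → 88.3 | 88.0 → 89.1 | 88.0 → 89.8 |

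The change runs from -0.4 to +2.1 points, with simulation error of about 0.5 to 0.7 points per estimate. The largest gain needs a steep effect: at 30%/18% and odds ratio 0.65, active clearance is about 50% with five lesions and 10% with ten. A second simulation (28% versus 15%, strata 5-7/8-10 by location, 20,000 trials per setting) gave -0.1 to +1.4 points.

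**Step 4: count alone in two bands, by hand.** From step 1 with independent lesions, mean P(clear) is 0.373 for 5-7 and 0.227 for 8-10. The variance explained is [(0.373 - 0.227)/2]² / 0.21 ≈ 2.5%, so the test statistic grows by about 1/√(1 - 0.025) ≈ 1.013. Unstratified power of 83.9% (28% versus 15%) corresponds to 1.96 + 0.99 = 2.95. Multiplying by 1.013 gives 2.99, hence power of about 84.8%, a gain of roughly 0.9 point. Stronger within-subject correlation makes it smaller.

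**Step 5: type I error.** With no treatment effect, rejection in favour of active was 1.4-1.9% unadjusted and 1.6-1.9% stratified (10,000 trials per setting), against a nominal 2.5%, whether or not count was prognostic.

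**Step 6: chance imbalance.** For counts uniform on 5-10, SD = √(35/12) = 1.71. The SD of the difference in mean count is 1.71 × √(2/139) = 0.20 lesion in PP and 1.71 × √(2/186) = 0.18 in mITT. The slope is (0.44 - 0.19)/5 = 0.05 per lesion for independent lesions and (0.36 - 0.26)/5 = 0.02 at correlation 0.4. In PP, one SD of imbalance therefore moves the difference by 0.4 to 1.0 point, against an equivalence margin of 20 points.

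**The case against.** The strongest reply is that nothing is wrong. No stratification by count or location is stated that the analysis would have to match, randomisation makes the unadjusted test valid, and its error rate already allows for chance imbalance. All of that stands, and step 5 agrees. Entry is also confined to 5-10 lesions, and the baseline tables would reveal an imbalance.

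It is also fair that the prognostic effect is inferred. A reader might take it as established that ten lesions clear less often than five, or that face and scalp differ. The documents report neither. The direction for count follows from the endpoint definition if the chance per lesion is similar; its size is unknown. Nothing supports location, so it should be optional.

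The gain is within or near simulation error in many settings and can be slightly negative when count carries no information. The change also reaches beyond the SAP, because the protocol prescribes the unadjusted test in two places.

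A logistic model with site terms would be a poor alternative. With about 28 sites and 2 × 186 = 372 mITT subjects per comparison, there are about 13 per site, and its error control was not checked here.

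What remains is that a variable already collected and probably related to outcome can be used at little cost, and that the choice is best made before unblinding.

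**Conclusion.** The point holds as an optional improvement. Both superiority tests are valid and leave baseline AK count unused. Stratifying on it would be expected to change power by about 0 to 2 points, with no type I error cost. This rests on assumed clearance rates of 25-35% on active and 12-20% on vehicle, equal arms of 186, and an assumed effect of count; the upper end needs a steep one.

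A reader might infer that the planned test is biased or anticonservative, or that the equivalence conclusion is at risk. The documents do not support either. The simulated error rate is below nominal, and a typical chance imbalance moves the PP difference by at most about 1 point against a 20-point margin. Imbalance produced by the PP exclusions cannot be sized from the documents, which is the reason for showing an adjusted difference beside the primary one.

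**What to change.** 1. In SAP 8.6.1, specify for each active-versus-vehicle comparison in mITT a Cochran-Mantel-Haenszel test stratified by total baseline AK count (5-7, 8-10), two-sided at 0.05. Use the same continuity correction: [|Σ(a - E(a))| - 0.5]² / ΣVar(a), summed over strata. Eligibility places every mITT subject in one of the two bands.
2. Keep the unadjusted chi-square, with the existing Fisher rule for sparse tables, as a sensitivity analysis. State which test applies if the stratified table is sparse.
3. Align protocol 17.3.1 and the synopsis. If the sponsor prefers not to change the primary test, make the stratified test supportive; the protocol wording for the primary test can then stand.
4. Report a count-standardised Test-Reference difference beside the primary Wald interval in PP, labelled supportive.
5. Treat location as optional, and do not add a logistic model with site.

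The cost is a few lines of protocol and SAP text and minor programming. No new data are needed, and the margin, endpoint, populations and equivalence test are unchanged.

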8.7 Dosing Compliance and Test Article Exposure

Test article compliance will be determined by the total number of test article applications verified from the data in the subject diaries. Compliant subjects are defined as those who apply at least 75% and no more than 125% of the expected (120) test article applications, did not miss more than 10 consecutive scheduled applications, and have no other evidence of material dosing noncompliance.

Descriptive statistics of the total number of applications, the number of missed applications, and the duration of treatment by treatment group will be presented for the Safety, mITT and PP populations.

8.8 Safety Analyses

8.8.1 Adverse Events

AE terms will be coded into SOC and PT using MedDRA Coding Dictionary version 19.0. Tabulations of the number and percent of unique subjects reporting each TEAE will be presented by SOC, PT, and treatment group for (a) AEs, (b) serious AEs, (c) AEs by maximum severity, (d) AEs by closest relationship to study drug and (e) AEs within treatment area. AEs will be counted only once for a subject within each PT and SOC. If a subject reports a PT multiple times with differing severities/relationships to study medication, the subject is counted once for the PT with the maximum severity and the closest relationship, respectively.

All adverse events will be listed.

8.8.2 Local Skin Reactions

The frequency of the individual LSRs (erythema, dryness/flaking/scaling, burning/stinging, erosion/ulceration, edema, pain, and pruritus) will be tabulated by severity and treatment group at Baseline, Day 30, Day 60 and Day 90/EOS.

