9.2 Visit 2 (Day 15 \pm 3 days): Phone Call

At this visit, the investigator or designee will:

- Query the subject about any changes in health status or any AEs since the last visit. Document in the AE section of the CRF, as appropriate. NOTE: If severe tolerability issues or a material AE concern of any type are noted, the subject may be scheduled for an in-office visit at the investigator's discretion.
- Record any changes in the subject's concomitant medications and therapies/procedures.
- Review the subject diary and test article compliance.
- Remind the subject to continue to apply test article twice daily, once in the morning and once in the evening, to the skin of the 25 cm² treatment area until the next clinic visit and to bring their tube of test article with them to their next clinic visit.
- Confirm the next appointment and instruct subject to not apply the study medication to the treatment area prior to any study visits.

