9.7 Unscheduled Visit

The investigator may see the subject at an unscheduled visit to manage any AEs or LSRs.

At this visit, the investigator or designee will:

- Query the subject about any changes in health status or any AEs since the last visit. Document in the AE section of the CRF, as appropriate.
- Use the transparency and the Baseline photo as necessary to locate the selected treatment area.
- Perform the LSR assessment as described in [Section 10.2](#).
- Record any changes in the subject's concomitant medications.
- Review subject diary and the requirements for test article application, if applicable.
- Confirm the next appointment.

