6 DEFINITIONS

- End of Treatment (EOT): Visit 5/Day 60
- End of Study (EOS): Visit 6/Day 90 or Early Termination Visit
- Study Day: The study day is the day of study relative to the date of randomization (Baseline visit/Day 1).
Study Day = follow-up visit date – randomization date + 1
- Baseline: The baseline assessment is defined as the last non-missing measurement collected at Baseline visit prior to the test article application.

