7.2.2 Local Skin Reactions Assessments

At Baseline, Day 30 follow-up, Day 60/EOT, Day 90/EOS, and Unscheduled Visits (if applicable), LSRs will be assessed in the 25 cm² Treatment Area using a four-point ordinal scale of 0 = absent, 1= mild (slight, barely perceptible), 2=moderate (distinct presence) and 3 = severe (marked, intense) for the following:

- Erythema
- Dryness/flaking/scaling
- Burning/stinging
- Erosion/ulceration
- Edema
- Pain (within the last 24 hours)
- Pruritus (itching) (within the last 24 hours)

These LSRs will be collected independently of AEs. LSRs that require medical intervention (e.g. prescription medication) or extend beyond the 5 cm surrounding skin will be documented as AEs.

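### The planned LSR tables leave out grades from unscheduled visits and cannot show each subject's worst grade

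*SAP*

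**What the plan says.** SAP 8.8.2 plans one kind of LSR summary: the frequency of each of the seven signs "will be tabulated by severity and treatment group at Baseline, Day 30, Day 60 and Day 90/EOS". The SAP list of tables matches this, with a Baseline LSR table (14.1.5) and one table per sign (14.3.2.1 to 14.3.2.7). No title points to a shift, worst-grade or unscheduled-visit table.

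Data collection is wider. SAP 7.2.2 states: "At Baseline, Day 30 follow-up, Day 60/EOT, Day 90/EOS, and Unscheduled Visits (if applicable), LSRs will be assessed". Protocol 9.7 gives the purpose of the extra visits: "The investigator may see the subject at an unscheduled visit to manage any AEs or LSRs". Protocol 9.2, and 9.4 in the same words, describe one trigger found at the Day 15 or Day 45 call: "If severe tolerability issues or a material AE concern of any type are noted, the subject may be scheduled for an in-office visit".

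LSRs are recorded apart from AEs. They cross over under one rule in SAP 7.2.2: "LSRs that require medical intervention (e.g. prescription medication) or extend beyond the 5 cm surrounding skin will be documented as AEs". For AEs, SAP 8.8.1 has a per-subject rule: when a preferred term recurs with different severities or relationships, "the subject is counted once for the PT with the maximum severity and the closest relationship, respectively". LSRs have no such rule.

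SAP 6 also defines "End of Study (EOS): Visit 6/Day 90 or Early Termination Visit".

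**The concern.** SAP 3 names LSR severity and frequency as a safety endpoint, and the protocol synopsis says LSRs are recorded so that the arms can be compared. Between Baseline and Day 60 the only scheduled grading is at Day 30, because Days 15 and 45 are telephone contacts. A reaction that flares and settles between clinic visits may be graded only at an unscheduled visit, and SAP 8.8.2 has no column for it. If it stays within the 5 cm border and is handled without prescription treatment, for example by holding doses, the AE rule does not require it to be recorded as an AE. It could then be absent from every LSR and AE table.

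Per-visit counts also describe the state of the skin on a given day. They do not say how many subjects were ever affected, or how badly. And because EOS includes early termination, the grade of a subject who leaves early and does not return at Day 90 falls in the Day 90/EOS column, even if it was recorded close to treatment.

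**Working it through.** The plan states no LSR figure to reproduce. The only document input is enrolment: about 600 subjects randomised 1:1:1, so 600 / 3 = 200 per arm. Every LSR count below is an assumption.

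**1. Where an unscheduled grade goes.** It is collected (SAP 7.2.2; Protocol 9.7 and 10.2). It is not one of the four time points in SAP 8.8.2, and the SAP has no rule mapping it to one of them. It enters an AE table only if the SAP 7.2.2 crossover rule applies. Otherwise it should appear only in Listing 16.2.7.3, which is by subject and not summarised by arm. Each such subject is 1/200 = 0.5 percentage points of an arm: 2, 4 or 10 subjects are 1, 2 or 5 points.

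**2. What per-visit counts say about worst grade.** Let n30 and n60 be the subjects at grade 2 or higher on Day 30 and Day 60, with all subjects assessed at both. The number affected at either visit lies between max(n30, n60) and n30 + n60.

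- 18 and 18: from 18 to 36 subjects, 9% to 18%.
- 9 and 9: from 9 to 18 subjects, 4.5% to 9%.
- If these were an active arm and vehicle, the difference in subjects ever affected could be anything from 18 − 18 = 0 to 36 − 9 = 27, that is 0 to 13.5 points.

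This holds for all seven signs and does not depend on Baseline grades.

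**3. Secondary point, dryness/flaking/scaling only.** Protocol 1 describes AKs as scaly, so Baseline scaling may not be zero. Scale that resolves as AKs clear could then offset new scaling. Let b be the share at Baseline grade 1, with the rest at grade 0. Assume new scaling at Day 60 in 30% of grade-0 subjects on active (8% at grade 2 or higher) and 15% on vehicle (4%). Assume resolution of grade 1 in r_A on active and 20% on vehicle, and worsening of grade 1 to grade 2 or higher in 10% and 5%.

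Any-grade difference = (1 − b) × 0.15 − b × (r_A − 0.20). With r_A = 0.40:

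| b | Any-grade difference (points) |
|---|---|
| 0% | +15 |
| 10% | 13.5 − 2 = +11.5 |
| 20% | 12 − 4 = +8 |
| 40% | 9 − 8 = +1 |

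At b = 40%, worse than own Baseline is 0.6 × 0.30 + 0.4 × 0.10 = 22% on active and 0.6 × 0.15 + 0.4 × 0.05 = 11% on vehicle. Grade 2 or higher is 0.6 × 0.08 + 0.4 × 0.10 = 8.8% against 0.6 × 0.04 + 0.4 × 0.05 = 4.4%, about 18 and 9 subjects. The planned table would show that doubling.

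**4. Limit of a worse-than-Baseline count.** Suppose new AKs cause scaling in 5% of otherwise unaffected grade-0 subjects on active and in a share v on vehicle. Active becomes 0.6 × (0.30 + 0.70 × 0.05) + 0.04 = 24.1%. Vehicle, 0.6 × (0.15 + 0.85v) + 0.02, becomes 13.55%, 16.1% or 21.2% at v = 5%, 10% or 20%. The difference of 11 points falls to 10.6, 8.0 or 2.9.

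**The case against.** The planned tables already report severity and frequency by arm, which is what the endpoint asks for, and randomisation makes the comparison at each visit valid. Both documents use the same by-visit layout. Reactions that need prescription treatment or spread beyond the border reach the AE tables by maximum severity (14.3.1.4) and within the treatment area (14.3.1.6). Discontinuation reasons are tabulated by arm, and Listing 16.2.7.3 gives subject-level LSR data. Protocol 17.3.2.3 refers to onsite clinic visits in general, which could be read to cover in-office unscheduled visits.

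Most of this stands, and it keeps the point small. It does not close the gap. The SAP names four time points that exclude unscheduled visits, a listing is not a comparison between arms, and none of the tables gives a worst LSR grade per subject.

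A reader might go further and infer that the by-visit tables hide an active-versus-vehicle difference because Baseline scaling resolves. The documents do not support that. It concerns one sign of seven. Near-complete offset needs about 40% Baseline prevalence and twice the vehicle's resolution rate, and neither figure has a source. Eligibility requires nonhyperkeratotic lesions and excludes confounding skin conditions. At 10% or 20% prevalence the difference still shows in the right direction, and even at 40% the higher grades show it.

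**Conclusion.** The point holds as a cheap improvement of minor severity. As written, the SAP leaves LSR grades from unscheduled visits out of every LSR summary table, and its per-visit counts cannot give each subject's worst grade, although AEs are summarised that way. On assumed counts of 18 and 18 out of 200, the share ever affected is known only to lie between 9% and 18%, and each subject graded 2 or higher only at an unscheduled visit is a further 0.5 points unseen. How often either occurs is unknown. Offset of Baseline scaling is a possible secondary issue of unknown size.

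A reader might also infer that data are lost or that the efficacy conclusions are at risk. Neither follows: the grades are collected, and the equivalence and superiority analyses do not use them.

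The conclusion rests on the SAP text and table titles, because table shells are not among the documents, and on about 200 subjects per arm.

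**What to change.** Keep the by-visit tables. Add to SAP 8.8.2, for each LSR and arm in the Safety population, a descriptive shift table of Baseline grade by worst post-Baseline grade, with the number and percentage above their own Baseline grade.

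- **Assessments used:** every LSR grading after first application through the upper limit of the Day 60/EOT window (60 + 4 = Day 64), including unscheduled and Early Termination assessments, whether or not the subject was still dosing. The window should not be tied to the last application. A subject who stops for irritation on Day 20 and returns at Day 30, as Protocol 13.2 asks, must still count.
- **Denominator:** subjects with a Baseline grade and at least one such assessment. Report per arm how many have none and how many had unscheduled assessments.

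The cost is SAP wording and seven tables from grades already collected, with no new data, visits or tests. Subjects with unscheduled visits get more looks, which is why their number should be shown. Scaling from new AKs may count as worsening, and a subject at grade 3 at Baseline cannot rise. If the table is added only after the SAP is final, SAP 2 would require it to be identified as unplanned in the study report.
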